5.16. Limitations of the study. The most important limitation derives from the fact that CGS technology is changing rapidly and it is being incorporated rapidly into clinical care. We will utilize the most advanced CGS technology that is available to us when we begin recruitment. While the various manufacturers protect their research and development plans due to the highly competitive business environment, it is clear that each company has a new iteration of its device in development. Our prior interactions with the manufacturers in the DirecNet and JDRF work have cultivated a climate of collaborative trust with these companies. The proposed research could be seen by the companies as useful to them in seeking FDA approval for pediatric indications for their devices and for expanding the marketability of CGS to adolescents with suboptimal glycemic control. Thus, there is a strong likelihood that the proposed study can utilize the most advanced CGS technology at the time enrollment would begin. Regardless of the specific CGS devices used, the study will still yield valuable information about enhancement of the capacity to derive glycemic benefits from this technology through the provision of a targeted behavior therapy intervention. The study could also inform other studies of the prediction and facilitation of benefit from technological advances in other medical contexts. Also, we will permit study participants to change to CGS devices that may emerge during the study, consistent with our intention of evaluating variables affecting the achievement of glycemic benefits from CGS use in a generic sense rather than a focus on evaluating or comparing specific CGS devices.

Another conceivable limitation is that the study design was driven in part by the desire to keep the direct costs for the project below \$500K in each year. This strategy was recommended by the NIDDK Program Officer responsible for behavioral science research. Completing the study in less than 5 years is not possible without exceeding that limit substantially or without major design changes.

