baseline. As would typify clinical practices at the participating sites, this will consist of offering monthly clinic visits with a diabetes nurse, weekly telephone consultation with the nurse and referral to a dietitian, social worker, psychologist or psychiatrist at the discretion of the treating endocrinologist. Fifth, an external Data Safety Committee will carefully monitor the safety of study participants, particularly with respect to the concerns about youths' decreasing the frequency of conventional SMBG to unsafe levels. Finally, CGS sensors will be distributed once each 2 weeks to patients and, if a youth fails to demonstrate an average of at least 3 SMBG checks per day in the intervals between these distributions, no further sensors will be supplied until adequate SMBG frequency has been restored. Together with the promising data on therapeutic efficacy and safety of CGS use discussed above, and these numerous procedural safeguards, we are confident that participants in the proposed trial will enjoy levels of glycemic control and freedom from foreseeable adverse events that are at least as favorable as those experienced by comparable patients who do not enroll in this study.

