Treatment of type 1 diabetes mellitus (T1DM) requires daily insulin injections or use of an insulin pump, self-monitoring of blood glucose (SMBG) several times daily, regulation of carbohydrate intake, regular exercise and correction of hyperglycemia and hypoglycemia.³¹ The outcomes of family management of pediatric T1DM reflect many psychosocial influences.³²⁻³⁵ Some youths and families negotiate these challenges effectively, but others endure poorer glycemic control, treatment adherence, family relations and quality of life during this period.³²⁻³⁵ Poor adaptation to T1DM in youth may persist into early adulthood, increasing the risks of long-term complications.³⁶⁻³⁷ Practical methods are needed to enhance the capacity of youths and parents to manage T1DM effectively. Continuous glucose sensors (CGS) have now been developed that provide continuous real-time data on glucose levels and trends. The CGS could benefit many adolescents with T1DM by providing more useful feedback on glycemic levels, direction and variability than is feasible with conventional SMBG.³⁸⁻⁴³ But, these benefits may depend on how well families can collaborate in using CGS data for therapeutic decision-making.⁴⁴⁻⁴⁵ While youths in sub-optimal glycemic control could benefit from CGS, the benefits could be enhanced if they received a specific, targeted behavioral intervention. Drawing on our prior studies, the proposed research will explore whether glucose regulation by youths with T1DM using CGS can be enhanced by a behavioral intervention targeting diabetes management behaviors of adolescents and parents/caregivers that are critical to effective CGS use. This application addresses these specific aims:

SPECIFIC AIM 1. In a 3-center sample of 150 adolescents with T1DM and HbA_{1C} of 7.5% to 10.0%, we will compare the effects of Standard Care (SC) alone or augmented by either CGS alone (CGS) or CGS plus a behavior therapy intervention designed to optimize CGS benefits (CGS+BT). Primary outcome measures will be HbA_{1C}, 7-day continuous glucose profiles, and indices of blood glucose variability and risks for severe hypoglycemia. Frequency of severe and moderately severe hypoglycemia will be secondary outcomes.

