Youths may be confused when CGS values differ from SMBG results or from "expected" values. Alarms signaling unwanted glucose fluctuations may intrude into activities that teens are unwilling to interrupt. False alarms, especially if repetitive, may induce adolescents to disregard the alarms. For teens whose self-care behaviors are inconsistent, their CGS results may also seem capricious, making it difficult to adjust the regimen effectively. CGS feedback could aggravate conflict between youths and parents about glycemic control. Hence, these potential "response costs" from CGS use may undermine its potential benefits. While CGS carries potential benefits, the above concerns suggest that incorporation of CGS into T1DM care may place a premium on family characteristics that influence the effectiveness of diabetes management.

In our prior studies of the GlucoWatch and Navigator, frequency of use of both devices declined steadily over time. The best estimates of frequency of use are from our Navigator pilot studies (See Section 4). Insulin pump patients used the Navigator for about 149 hours per week (88% of maximal) in the first 4 weeks, but this declined to 134 hours per week during the last 4 weeks of the 13 week study (80% of maximal). Children on MDI therapy used the Navigator slightly more often initially (153 hours/week) but declined more rapidly to 109 hours per week (65% of maximal) by the last 4 weeks. Given that MDI patients have actively decided against the use of one T1DM device (insulin pump) it is not surprising that they would be somewhat less enthusiastic than pump patients about use of CGS. Since we plan to enroll youths with suboptimal glycemic control and follow them longer, frequency of CGS use may decline more rapidly and to lower levels in this study. Thus, there are many behavioral variables that may impact effective use of CGS technology. Teens who are already struggling with T1DM management may be at the highest risk of counterproductive behavioral reactions to CGS use. Yet, these same youths could also derive the most therapeutic benefits from CGS if these impediments can be anticipated and prevented and if more positive and constructive behaviors can be encouraged. The behavioral intervention proposed for this study is designed to achieve these effects.

[figure not shown]

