DirecNet completed a randomized, controlled trial of the GlucoWatch Biographer (GWB), with HbA_{1c} and "blinded" use of the Medtronic CGMS as primary outcomes.⁵⁶ A sample of 200 highly motivated, compliant T1DM patients with mean baseline HbA_{1c} of 7.9% was randomized to SMBG alone or augmented with GWB use for 6 months. The study showed that the GWB did not affect glycemic control, hypoglycemia, quality of life, or adherence. GWB use declined steadily and 26% of patients stopped using it. Skin problems, gaps in data, inaccuracy, and calibration failures limited benefit from the device.

DirecNet also evaluated the accuracy of the Freestyle Navigator⁶² and completed pilot studies of its clinical utility among 30 youths with T1DM on insulin pumps² and 27 youths on multiple daily injections.³⁻⁴ Complete data are available for 13 weeks' use of the Navigator for 51 of the 57 children who enrolled. A total of 9 patients stopped using the Navigator within 13 weeks, 2 on insulin pumps and 7 on MDI regimens. Mean HbA_{1c} declined significantly for pump patients ($p < .01$) and for MDI patients ($p < .04$) over 13 weeks, with larger decreases among patients with higher baseline HbA_{1c} on either regimen. Further slight decreases in HbA_{1c} have been observed among the patients who have continued using the Navigator for up to 18 months. *There was no change in the frequency of severe hypoglycemia relative to the 6 months prior to enrollment for either sub-sample, showing that reduction in HbA_{1c} was not accompanied by increased risk of severe hypoglycemia. Scores on the Continuous Glucose Monitor Satisfaction Scale were uniformly positive for both pump and MDI participants.* Among pump patients, the added Navigator burden did not adversely affect quality of life for parents or children. Youths on MDI regimens, but not their parents, reported significantly improved scores on the PedsQL Diabetes Module¹³⁶ after 13 weeks of CGS use. All of these results should be interpreted in context, since the enrolled children and parents were carefully selected and highly motivated and may not be representative of the broader clinical population.

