One-Week "Blinded" CGS Use As in the JDRF Artificial Pancreas Project, prior to randomization, each family will be given a "blinded" CGS device (glucose feedback disabled) to use for 7 days and to return to the clinic for downloading. A minimum prerequisite for randomization will be at least 96 hours of analyzable CGS data. In addition to providing valuable data, this will serve as a "run-in" period to screen out participants who cannot comply with basic requirements and enable them to withdraw if they find CGS use to be intolerable (6 of 451 JDRF participants did so). Blinded CGS use will recur at 3, 6 and 9 months. CGS data obtained from SC participants in this manner will be compared to comparable data obtained during CGS use by those in the CGS and CGS+BT groups. Periodic 7-day samples of CGS data will be randomly selected from these participants' downloaded CGS data from within the month prior to each quarterly clinic visit.

Hemoglobin A_{1c} and other medical variables Finger-stick blood samples will be obtained for central laboratory HbA_{1c} assays at Baseline and each 3 months. For eligibility verification and clinical use, HbA_{1c} will be measured on DCA-2000 analyzers (Bayer Diagnostics Inc.) at each site as usual.¹⁴⁶ Blood samples will be obtained at each quarterly visit and sent to the Baptist Medical Center lab in Jacksonville using the sample collection and shipping protocol that is currently used in the FMOD trial. Assays will be run on a Tosoh Analyzer using cation-exchange HPLC to separate hemoglobin fractions, including stable A_{1c}, by a buffer gradient of increasing ionic strength. Coefficients of variation range from 2-3%. Several studies have shown high correlations between HbA_{1c} measured by DCA-2000 versus central labs using such HPLC, but there is consistent bias in DCA-2000 results so that central lab measurement is needed.¹³² Other medical variables that will be obtained quarterly include Tanner Stage (breasts for females; genitalia for males; pubic hair for both), height, weight, Body Mass Index, linear growth velocity, and details of T1DM regimens.

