Glucose meter with memory All patients with T1DM at these clinics use glucose meters with memory, enabling storage of SMBG results by date and time. Downloading stored data provides a complete record of the patient's SMBG results. Patients will bring their meters to all clinic visits for downloading and discussion of treatment changes. Adolescents will receive a \$10 gift card at each clinic visit if they bring their blood glucose meters with them for downloading, a procedure that has yielded 94% adherence in the FMOD trial.

Downloaded data will yield descriptive statistics and measures of glycemic variability described below. The project will provide SMBG test strips to those without insurance coverage for them.

Continuous Glucose Sensor Diabetes Nurses will be trained by representatives of each CGS company, and with an on-line curriculum that will soon be on the JDRF website.¹⁴⁹ [name], R.N, a Diabetes Nurse in the JDRF Artificial Pancreas Project, will coordinate bi-weekly video-conferences for study nurses before enrollment and monthly case discussions in the first 2 years. Patients in the CGS and CGS+BT groups will select, with the help of diabetes nurses and physicians, the available CGS device that best matches their preferences for use during the study. The devices and supplies will be provided without charge. The same will apply to SC participants during the 3-month Continuation Phase. For the CGS and CGS+BT groups, a 7-day continuous sample of CGS data will be selected randomly from the months prior to the 3-month, 6-month and 9-month study visits to provide profiles for direct comparison to blinded CGS data for the SC group. Adolescents will be paid \$10 for downloading the CGS device and sending the data to the coordinating center monthly. In the DirecNet and JDRF studies, virtually all families have been able to arrange this using either their own computers or one owned by a relative, neighbor or employer. The study will provide a home computer, internet access and training for up to 15 low-SES families.

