5.7. Measurement schedule. In the measurement schedule below, "P" indicates collection of the measure from parent, "A" = from adolescents and "B" = from both parents and youths. All measures will be translated into Spanish and back-translated into English by native Spanish speakers. Participants may choose whether to complete the English or Spanish versions. Internal consistency and test-retest reliability will be calculated for each measure based upon data collected in the proposed study.

MEASUREMENT SCHEDULE

Measure	Study Visits (Months)				
	0	3	6	9	12
General Information Form (P)	•				
Glucose Meter memory downloads (A)	•	•	•	•	•
CGS Device downloads (A)	•	•	•	•	•
Measures of glycemic variability (A)	•	•	•	•	•
Hypoglycemia Diary (B)	•	•	•	•	•
HbA _{1c} (A)	•	•	•	•	•
7-Day Blinded CGS use (SC only)	•	•	•	•	•
Diabetes Self Management Profile (B)	•	•	•		•
Glucose Monitoring System Rating Scale (B)	•	•	•	•	•
BG Monitoring Communication Questionnaire	•	•	•	•	•
Hypoglycemia Fear Survey (B)	•	•	•	•	•
Diabetes Family Responsibility Questionnaire (B)	•	•	•	•	•
Wiebe Parental Involvement Interview (A)	•	•	•	•	•
Diabetes Responsibility & Conflict Scale (B)	•	•	•	•	•
PedsQL Diabetes Module (B)	•	•	•	•	•
Readiness to Change Questionnaire (B) (CGS+BT only)	•	•	•	•	•
Diabetes Problem Solving Interview (B)	•				

The only copyrighted instrument being administered is the PedsQL quality of life questionnaire, but Nemours owns a site license that permits free use and distribution for research purposes at all Nemours entities. Consequently, it will be possible to enable administration of the various measures via a secure internet connection using the Opinio software platform. This functionality will enable participants to complete questionnaires from anywhere that provides internet access at any time within the 2 week period immediately preceding each quarterly diabetes clinic visit. If participants are unable to accomplish this, the questionnaires will be available for hard-copy administration at clinic visits and they will be encouraged to do so during waiting times before and during their visits. This flexibility should enable participants to control the amount of time dedicated to study participation on clinic visit days.

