Statistical analysis will begin with treatment of missing data, preliminary descriptive analysis and visual inspection of distributions.¹⁵⁵⁻¹⁵⁶ Appropriate transformations of variables will be used to restore normality if needed. Baseline values of the primary outcome and predictor variables will be compared to determine if there are significant pretreatment differences between the groups that require adjustments. Visual examination of scatter plots, histograms and other graphical summaries will be used to identify possible associations or treatment effects of interest. Where multiple statistical comparisons are planned, we will make appropriate multiplicity adjustments.¹⁵⁵⁻¹⁵⁸ Internal consistency will be calculated for each psychometric measure based on

data from this study and only those with $\alpha \geq .70$ will enter data analyses. Upon completion of these preparatory activities, we will apply Individual Growth Modeling¹⁶⁰⁻¹⁶¹ to test the hypotheses listed below (see Section 5.12 for details).

5.10. Hypotheses. The following hypotheses, corresponding to the three specific aims, will be tested:

Hypothesis 1: Adolescents in CGS+BT will show more improvement in glycemic control (HbA_{1C}, Kovatchev's measures of glycemic variability derived from SMBG and CGS data, and proportion of CGS values in the normal range) compared with those in SC and CGS over the 9-month Randomized Phase.

Hypothesis 2: Adolescents in CGS+BT will realize more improvement in diabetes-related behavioral outcomes (Diabetes Self-Management Profile; PedsQL Diabetes Module; Diabetes Responsibility and Conflict Scale; Hypoglycemia Fear Survey; Blood Glucose Monitoring Communication Questionnaire: Blood Glucose Monitoring System Rating Questionnaire) compared with those in SC and CGS and in scores on the CGM Satisfaction Scale (CGS vs CGS+BT only) over the 9-month randomization phase of the study.

Hypothesis 3a: Improvements in HbA_{1C} during the 9-month Randomized Phase will be moderated by adolescents' and parents' baseline status on the following measures: Socioeconomic status; Family composition; Adolescent age; Diabetes Problem Solving Interview, Parent-Adolescent Relationship Questionnaire; Diabetes Family Responsibility Questionnaire; Wiebe Parental Supportive Involvement Interview; and Diabetes Responsibility and Conflict Scale).

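### Sensor outcomes come from a scheduled wear in Standard Care but only from ongoing clinical sensor use in the two CGS arms, with no fallback when a youth is not wearing one

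*Combined protocol and SAP*

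**What the plan says.** Specific Aim 1 (Section 2) states: "Primary outcome measures will be HbA_{1C}, 7-day continuous glucose profiles, and indices of blood glucose variability and risks for severe hypoglycemia". Hypothesis 1 (Sections 5.10 and 5.12) adds "proportion of CGS values in the normal range". Section 5.13 names HbA1c as the primary outcome for the power calculation.

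Section 5.5 gives the sensor outcomes two sources after baseline:

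- **Standard Care:** a 7-day blinded wear, scheduled at 3, 6 and 9 months.
- **CGS and CGS+BT:** downloads of the youths' own real-time use. The Standard Care data "will be compared to comparable data obtained during CGS use by those in the CGS and CGS+BT groups", and for those arms "a 7-day continuous sample of CGS data will be selected randomly from the months prior to the 3-month, 6-month and 9-month study visits". The paragraph on blinded use puts the sampling window at the month before each visit.

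The schedule in Section 5.7 labels the row "7-Day Blinded CGS use (SC only". The 96-hour minimum of analyzable data in Section 5.5 is a condition for randomization; none is stated for follow-up in any arm.

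Section 1 adds a supply rule. If a youth averages fewer than 3 fingerstick checks a day between the two-weekly distributions, "no further sensors will be supplied until adequate SMBG frequency has been restored".

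**The concern.** In the CGS arms, whether a sensor outcome exists at a visit depends on what the youth did after randomization, and on whether sensors were being supplied. In Standard Care every youth is offered the measurement, however adherent. The plan gives no substitute wear for a CGS-arm youth who has stopped, and no rule for a visit without a usable week.

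The plan expects wear to fall. Section 3.5 says that "frequency of CGS use may decline more rapidly and to lower levels in this study". In the pilots in Section 4.2, "A total of 9 patients stopped using the Navigator within 13 weeks", and those families were described as carefully selected and highly motivated.

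If the youths who stop are also those whose glucose is doing worse, the CGS-arm profiles lean toward better-controlled youths and the Standard Care profiles do not. That would favour CGS over Standard Care on an outcome Aim 1 calls primary. Sensor data that were never collected cannot be recovered in analysis.

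**Working it through.** **The plan's own figure.** No power or sample size is stated for the sensor outcomes. The 94.5% in Section 5.13 is for HbA1c, CGS versus CGS+BT. A two-mean comparison with its inputs (difference 0.8, SD 1.5, 50 per arm, two-sided 5% assumed) gives 76.0%. A linear growth model comes within 2 points of 94.5% only for some variance components that the plan does not state. The figure is attainable but cannot be verified, and nothing below uses it.

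**Inputs from the documents**

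- Retained at month 9: 45 per arm (Section 5.13).
- Navigator stopped within 13 weeks (Section 4.2): pump 2/30 = 6.7%; MDI 7/27 = 25.9%; pooled 9/57 = 15.8%.
- GlucoWatch stopped in a 6-month trial (Section 4.2): 26%.
- Analysis: growth model on all available measurements (Section 5.12).

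**Step 1. Month-9 profiles per CGS arm**, 45 × (1 − p):

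- p = 6.7%: 42.0
- p = 15.8%: 37.9
- p = 26%: 33.3

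Standard Care has up to 45. These rates cover 13 weeks or 6 months in other samples. The 9-month rate here is not given, and losses from the supply rule would come on top.

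**Step 2. One-visit comparison of wearers with no true effect.** Let ρ be the assumed correlation between wear and the glucose outcome, and let those least inclined to wear be missing. The shift in the retained mean is ρ·φ(z_p)/(1 − p), where φ(z_p)/(1 − p) is 0.286 at 15.8% and 0.438 at 26%. The standard error is √(1/45 + 1/(45(1 − p))).

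| p | ρ | Shift (SD) | Two-sided type I error |
|---|---|---|---|
| 15.8% | 0.3 | 0.09 | 6.8% |
| 15.8% | 0.5 | 0.14 | 10.0% |
| 26% | 0.3 | 0.13 | 8.9% |
| 26% | 0.5 | 0.22 | 16.0% |

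**Step 3. The kind of analysis the plan specifies.** A linear growth model at months 0, 3, 6 and 9 was simulated under no effect: 45 per arm, 3,000 runs, stopping in one arm only. Assumed variances were intercept 0.7, slope over 9 months 0.3 and residual 0.3, so the baseline variance is 1. Of those who stop, 60% have only the baseline, 20% also month 3, and 20% also months 3 and 6. Here ρ is the correlation between stopping and the youth's own glycemic trend.

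| p | ρ | Bias favouring CGS (baseline SD) | Type I error |
|---|---|---|---|
| 15.8% | 0 | 0.00 | 4.9% |
| 15.8% | 0.3 | 0.04 | 6.1% |
| 15.8% | 0.5 | 0.07 | 6.0% |
| 26% | 0 | 0.00 | 4.8% |
| 26% | 0.3 | 0.06 | 6.5% |
| 26% | 0.5 | 0.11 | 7.0% |

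Simulation error at 7% is about 1.96 × √(0.07 × 0.93/3000) = 0.9 points. Because ρ refers to the trend here and to the visit's value in Step 2, the gap between the two tables is not purely the benefit of the model.

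**Step 4. Loss in Standard Care as well.** If Standard Care lost an assumed 10% by the same mechanism, φ(z_p)/(1 − p) = 0.195, or 0.06 to 0.10 SD for ρ = 0.3 to 0.5. The net Step 2 shifts become 0.086 − 0.058 = 0.03 to 0.143 − 0.097 = 0.05 at 15.8%, and 0.131 − 0.058 = 0.07 to 0.219 − 0.097 = 0.12 at 26%.

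**The case against.** The strongest reply is that little is lost. A youth who stops keeps the blinded baseline and earlier visits in the growth model, and keeps HbA1c and the SMBG-based indices, which Section 5.5 calculates for all groups. Entry rules (at least 3 SMBG checks a day, Section 1; the 96-hour run-in, Section 5.5) screen out the least adherent in every arm. Supply is withheld only until testing recovers. Late wear in the pilots still averaged 109 to 134 hours a week (Section 3.5). All of this stands and limits the size. None of it supplies a sensor outcome for a visit at which a CGS-arm youth was not wearing a sensor.

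It can also be said that Section 5.5 has blinded use recur without naming an arm, and that the schedule label cannot be exact at month 0, since Section 5.8 has every participant do the run-in. But both descriptions of follow-up in Section 5.5 take the CGS-arm week from downloads, which agrees with the label.

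Some stronger readings are tempting but not supported:

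- **Type I error of 9 to 16%.** A reader might infer this from Step 2. It belongs to a raw one-visit test that the plan does not propose, with no Standard Care loss, and it leaves out the 6.8% corner.
- **Standard Care is measured in everyone.** Being scheduled is not supplying data. Those youths can miss a wear, and no follow-up minimum binds them either.
- **Any gap means no profile.** No rule rejects partial wear. With sensor lives of 72 and 120 hours plus warm-up on two of the three devices (Table 1), a literally gap-free week cannot be meant.
- **CGS+BT is penalised against CGS.** The therapy targets inadequate sensor use (Section 5.8), so retention of poorer users could differ, but only if therapy sustains wear. The direction is open and no size can be given.

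**Conclusion.** The asymmetry is in the text, and nothing found in the documents repairs it. It affects the 7-day profiles, the proportion in range and the sensor-based indices, at the affected visits only. HbA1c is untouched. The documents list the profiles as primary in Aim 1 but do not use the term co-primary, so the point should not be read as undermining the powered comparison.

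The size is modest: about 0.04 to 0.11 SD in favour of CGS, with type I error of about 6 to 7%, under the planned model at 16 to 26% loss. This rests on an assumed correlation of 0.3 to 0.5, assumed variance components, no loss in Standard Care, and stopping rates from other samples. The 26% GlucoWatch figure is for a device not offered here. With zero correlation there is no bias, and missed wears in Standard Care would shrink it. Longer follow-up and the supply rule could raise the loss by an unknown amount. It is worth correcting because measuring a listed primary outcome in the same way in all arms is cheap.

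**What to change.** In Section 5.5 and the Section 5.7 table:

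1. Schedule the same 7-day measurement wear at 3, 6 and 9 months in all three arms, with the 96-hour analyzable minimum applied at each of these visits.
2. Use a blinded sensor for youths not currently using, or not being supplied, sensors. It gives them no feedback, so the clinical supply rule stays as written.
3. Base the Hypothesis 1 sensor outcomes on this wear, and keep weeks cut from clinical use as descriptive.
4. Report by arm and visit how many participants supplied a profile.

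The cost is a wording change and one sensor-week per visit for CGS-arm youths not wearing one; the devices, downloads and blinded procedure are already in the study. Non-users carry a small extra wear burden and some will decline, so selective missingness is reduced, not eliminated.
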